Stress induced craving paradigm. The pathophysiology of nicotine dependence includes the interaction between stress, environment and body physiology, fuelling the illness(63). Multiple previous studies have modeled craving for nicotine in the presence of stress, to approximate real world scenarios(64-66). Before we test TBS as a clinical intervention, we will explore whether one session of TBS can modulate craving in the context of induced stress. Two promising paradigms for stress induction are the cold pressor test (CPT) wherein participants immerse their feet in ice cold water (2-4 degree Celsius) for three minutes and the paced serial addition task (PASAT)(67). The cold pressor test invokes an immediate cardiovascular stress response, initiated by the sympathetic nervous system, followed by a neuroendocrine response controlled by the hypothalamus-pituitary-adrenal (HPA) axis(67). The PASAT is a cognitively challenging task and will be performed in parallel with the CPT as an additional means for stress induction. The task requires participants to listen to a standardized audio-recording of a series of single-digit numbers and to say aloud the sum of the last two numbers presented (within each inter-trial interval). The PASAT will also last less than three minutes. Peak stress response occurred 20 minutes after these paradigms were performed(67). In our pilot study, these paradigms will be performed simultaneously, and followed by the tobacco craving questionnaire (TCQ).

Brain network connectivity to complement attentional bias modulation. Neuroimaging has shown resting state functional connectivity (rsFC) changes in patients who smoke(68). This encompasses connectivity changes in default mode network, executive control network and salience network. Previous studies have shown a negative correlation between smoking behavior severity and connectivity in the dorsal anterior cingulate (dACC)- ventral striatum (VS) circuit(68). Previous studies have also shown the salience network to be deeply involved in the regulation of attention to smoking cues versus neutral cues(68). Given that neuroimaging could potentially corroborate attentional bias modulation with TBS, we will attempt to explore correlations between changes in attentional bias and salience network as well as between changes in stress induced craving and connectivity in the dACC-VS circuit.

References

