74. Alcorn JL, 3rd, Strickland JC, Lile JA, Stoops WV, Rush CR. Acute methylphenidate administration reduces cocaine-cue attentional bias. *Prog Neuropsychopharmacol Biol Psychiatry*. 2020;103:109974.

Objectives

List your research objectives. Please include a summary of intended research objectives in the box below.

Before the study proper, we will conduct a pilot study to validate our attentional bias task in healthy controls who may or may not have a history of current or active smoking. The specific aim of this pilot would be to show differences in attentional bias between smokers and non smokers.

Study proper. Specific Aim 1 will demonstrate whether one session of MRI targeted TBS to left dorsolateral prefrontal cortex (DLPFC) will decrease attentional bias to smoking cues, compared to sham TMS. Subjects will receive both one TBS session (1800 pulses) and one session of sham TMS, lasting 10 minutes on separate days. They will perform an attentional bias task before and after TBS. We hypothesize that TBS will significantly decrease post session attentional bias to smoking cues compared to sham TMS.

Specific Aim 2 will demonstrate whether one session of TBS versus sham TMS, to left DLPFC can modulate stress induced craving for smoking. Subjects will perform the short form of tobacco craving questionnaire (TCQ-SF) before and after TBS. We hypothesize TBS will significantly decrease craving in smoking patients compared to sham TMS.

Specific Aim 3 will demonstrate whether one session of TBS versus sham TMS, to left DLPFC can increase seed based functional connectivity (fc) in the ventral striatum. We will acquire resting state functional MRI (fMRI) scans before and after TBS in all subjects. We hypothesize increase in fc in the dorsal anterior cingulate – ventral striatum circuit after TBS.

Study Design

Describe and explain the study design (e.g., observational, secondary analysis, single/double blind, parallel, crossover, deception, etc.).

- **Clinical Research:** Indicate whether subjects will be randomized and whether subjects will receive any placebo.
- **Community-Based Participatory Research:** If you are conducting community-based participatory research (CBPR), describe strategies for involvement of community members in the design and implementation of the study, and dissemination of results from the study.

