A sequential timeline of assessments and interventions are shown in table one. After informed consent, subjects will get an MRI brain scan at the Magnetic Resonance Imaging and Spectroscopy Center (MRISC) affiliated with University of Kentucky. Subjects will also be escorted to the MRISC at the UK Medical Center by the PI ([name]) and a research assistant. Subsequently, neuroimaging data (MRI brain) will be acquired using a Siemens 3-Tesla (3T) PRISMA MRI scanner as described under Data Collection below. This will happen on day 1. Then, on days 2 and 3, subjects will be scheduled for three hour experimental sessions at the TMS Suite at [name]. During these three hour sessions, subjects will perform the tobacco craving questionnaire (TCQ) while performing stress induced craving paradigm, attentional bias task and delayed discounting task. These activities will last an hour. Then we will obtain active motor threshold (AMT) from the first dorsal interosseous (FDI) muscle and left motor cortex, following which we will administer either a session of theta burst stimulation (TBS) for 9 minutes at 80% active motor threshold (AMT) or sham TMS to the left dorsolateral prefrontal cortex using a figure 8 coil and MagVenture MagPro x100 device (MagVenture A/S, Denmark), with TMS coil position stabilized using BrainSight (Rogue Solutions, Montreal, Canada). We will record motor evoked potential before and after the TBS session to assess response (10% increase in MEP to be a cutoff parameter). These activities will last another hour. After the TBS/sham TMS session, subjects will perform TCQ concomitant with the stress induced craving paradigm, attentional bias and delayed discounting tasks. These will last an hour. Then subjects will be transported to MRISC for their post TBS session MRI brain scan in the 3-Tesla (3T) PRISMA scanner.

Table 1

Study Task Study Day Pre- TBS Post-TBS

Urine Pregnancy Test 1

MRI brain at MRISC (Pre-TBS) 1

Exhaled CO 2 and 3 X

Motor Threshold 2 and 3 X

Eye tracking to measure AB 2 and 3 X X

Delayed Discounting Task 2 and 3 X X

Tobacco Craving Questionnaire 2 and 3 X X

TMS Side Effects Questionnaire 2 and 3 X

Treatment Acceptability Questionnaire 2 and 3 X

MRI brain at MRISC (Post-TBS) 2 and 3 X

Attachments

Subject Recruitment Methods & Advertising

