Cigarette craving analyses. TCQ-SF scores will be entered into a linear fixed effects regression model. Outcome variables for this model will be TCQ-SF score.

Resting state functional connectivity (rsFC) analyses. CONN functional connectivity toolbox (version 21.a) will be used for all preprocessing and neuroimaging analyses using standard procedures. Firstly, general linear model (GLM) analyses will explore if rsFC changed from two seeds (L. dIPFC and right insula) to all voxels following iTBS versus sham iTBS relative to baseline rsFC in participants who receive iTBS and sham iTBS. In first level analyses, a seed map will be created for every subject using respective seeds (L. dIPFC or right insula). In second level analyses, a between conditions contrast will be used to assess rsFC within-subject differences baseline, and following iTBS and sham ITBS. All second level analyses will use cluster level inferences based on Gaussian Random Field Theory. This will be done using general linear models (GLM) to generate a statistical map of t-values, that will subsequently threshold to reveal non overlapping clusters (<https://web.conn->

toolbox.org/fmri-methods/cluster-level-inferences). Two-sided p-values will be generated using cluster-level false discovery rate (FDR) correction ⁶².

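### Aim 3 predicts increased dACC–ventral striatum connectivity, but the planned connectivity analysis seeds only the left dlPFC and right insula and so never estimates that connection

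*Combined protocol and SAP*

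**What the plan says.** In the Objectives, Specific Aim 3 has two sentences that matter here. The general one asks whether one session of TBS, compared with sham, "can increase seed based functional connectivity (fc) in the ventral striatum". The specific one is the hypothesis: "We hypothesize increase in fc in the dorsal anterior cingulate – ventral striatum circuit after TBS".

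The background section on brain network connectivity explains why this circuit was chosen. It cites earlier work showing a "negative correlation between smoking behavior severity and connectivity in the dorsal anterior cingulate (dACC)- ventral striatum (VS) circuit", and it says the investigators will try to explore correlations between "changes in stress induced craving and connectivity in the dACC-VS circuit".

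The analysis text under the heading on resting state functional connectivity examines whether "rsFC changed from two seeds (L. dIPFC and right insula) to all voxels following iTBS versus sham iTBS relative to baseline rsFC". At first level, "a seed map will be created for every subject using respective seeds (L. dIPFC or right insula"). The second level contrasts conditions within subject, with two-sided p-values and whole-brain cluster-level FDR correction. It names no region of interest, mask or small-volume search.

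Table 1 in the Study Design section gives the scan schedule: "MRI brain at MRISC (Pre-TBS) 1" for the baseline scan and "MRI brain at MRISC (Post-TBS) 2 and 3 X" for the scans after each session.

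**The concern.** A seed-to-voxel map estimates how strongly the seed is connected to each voxel. It does not estimate how strongly two other regions are connected to each other. To estimate dACC–VS connectivity, one of those two regions must be the seed, or the two must be entered as a region pair. The plan does neither.

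Two consequences follow. First, no planned result can support or contradict the stated hypothesis, and the exploratory correlation with stress-induced craving has no specified connectivity measure. Second, two whole-brain maps leave room for a surviving dlPFC or insula cluster to be reported as the answer to Aim 3, or for a dACC–VS method to be chosen after the data are seen.

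**Working it through.** **1. Hypothesis against analysis.** The documents give no alpha, effect size or power figure for Aim 3, so there is no stated figure to reproduce. The check is a comparison of texts.

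| Place | Regions named |
|---|---|
| Objectives, Aim 3 general sentence | VS |
| Objectives, Aim 3 hypothesis | dACC and VS |
| Background, brain network connectivity | dACC–VS, to be correlated with craving change |
| Data Collection, fMRI | acquisition and preprocessing only |
| rsFC analyses | left dlPFC and right insula, each to all voxels |

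Neither of the 2 planned seeds is in the hypothesised pair. The planned maps can show change in dlPFC–VS, insula–VS, dlPFC–dACC and insula–dACC connectivity. They do not contain dACC–VS.

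**2. Can dACC–VS be inferred from the seed values?** Let *a* be the vector of dACC correlations with the two seeds, *v* the same for VS, and *R* the correlation matrix of the seeds. For the full correlation matrix to be valid, r(dACC,VS) must lie within

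a′R⁻¹v ± √[(1 − a′R⁻¹a)(1 − v′R⁻¹v)].

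The documents give no correlations, so these are assumptions: the seeds correlate 0.3 with each other, and every seed-to-region correlation equals r. All three quadratic forms then equal q = 2r²/1.3. The lower limit is q − (1 − q) = 2q − 1, and the upper limit is q + (1 − q) = 1.

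| r | q | Possible range of r(dACC,VS) |
|---|---|---|
| 0.1 | 0.02/1.3 = 0.0154 | -0.969 to 1.00 |
| 0.3 | 0.18/1.3 = 0.1385 | -0.723 to 1.00 |
| 0.5 | 0.50/1.3 = 0.3846 | -0.231 to 1.00 |

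The seed values leave the hypothesised quantity almost unconstrained.

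**3. A concrete case.** Hold the seed-to-seed correlation and all seed-to-region correlations at 0.30, and let dACC–VS rise from 0.10 after sham to 0.40 after iTBS. Both 4 × 4 correlation matrices are valid: their smallest eigenvalues are 0.592 and 0.600, both positive. The hypothesised effect could therefore occur with no change in either seed map at the dACC or the VS.

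**4. The baseline scan (a smaller point).** The second-level sentence also lists baseline as a condition. There is one Day 1 scan per subject, so (iTBS − baseline) − (sham − baseline) = iTBS − sham. Baseline has weight 0 and the main contrast is unaffected. A separate condition-minus-baseline contrast would be affected, because on Days 2 and 3 the scan follows the stressor and task blocks, whereas the Day 1 scan does not.

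**The case against.** The strongest reply is that Aim 3's general sentence is covered. The left dlPFC is the stimulated site, VS voxels are among all the voxels in its map, and a dlPFC–VS difference between iTBS and sham would bear on whether stimulation changes VS connectivity. That stands, although the plan does not single out the VS within the whole-brain search. It does not reach the hypothesis, which concerns a different connection.

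It can also be said that the analysis paragraph opens as the first of a sequence, that the statistical text may be an extract, and that the application lists protocol attachments not seen here. This limits the finding to the supplied text. No second step appears there, and a step that is not written down is not prespecified.

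A third reply is that this is a small pilot, connectivity is its third aim, and the seed maps are already worded as exploratory. That argues against a graver rating. It does not remove the problem: Aim 3 is worded as something the study will demonstrate and carries a directional hypothesis, so it needs an analysis that estimates the stated quantity.

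Finally, the correlations in the working are assumed and do not measure bias or power in this trial. That is correct. They only show that the planned maps cannot stand in for the missing one, and the mismatch does not depend on them.

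**Conclusion.** The concern holds for the documents supplied. The dACC–VS hypothesis has no specified test, and the exploratory craving correlation has no specified connectivity input. This is more than missing detail, because following the analysis text exactly yields no estimate of the hypothesised quantity. The text comparison alone establishes this. The numerical ranges rest on the assumed correlations and illustrate how little the two seed maps say about the missing connection. It should be fixed, but its reach is limited: Aims 1 and 2 are unaffected, and the iTBS-versus-sham contrast for the planned seeds is sound as regards the shared baseline.

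**What to change.** Choose one of two routes.

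- **Add the test.** Name one dACC–VS contrast as the Aim 3 analysis, either ROI-to-ROI or with one region as seed and the other as target region. Compare post-iTBS with post-sham within subject, with a period term for the crossover. Use the same measure in the exploratory craving correlation, and label the dlPFC and right-insula whole-brain maps exploratory.
- **Restate the hypothesis.** Reword the Aim 3 hypothesis so that it matches the planned seeds.

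Date either change relative to unblinding, and label it post hoc if it came afterwards. This matters in practice because the application is marked closed. Treat any separate condition-minus-baseline contrast as descriptive.

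The cost is some plan wording plus one ROI analysis on scans the protocol already provides for, or a one-sentence restatement. The only downside of the first route is that the dlPFC and insula maps are formally exploratory.
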